26 MAR 2019 Version no. 2.0 Page: 4 of 60

Signature of principal investigator

Name:		
Affiliation:		
Date:	Signature:	

In the protocol document, this page may remain unsigned.

center's investigator site file.

26 MAR 2019 Version no. 2.0 Page: 5 of 60

2. Synopsis

Title	LowEr Administered Dose with highEr Relaxivity: Gadovist vs Dotarem		
Acronym	LEADER 75		
Clinical study phase	Phase 4		
Study objective(s)	The primary objectives of this study are to demonstrate:		
	Noninferiority of gadobutrol (0.075 mmol/kg BW) compared to gadoterate (0.1 mmol/kg BW) based on a blinded read for:		
	Degree of contrast enhancement		
	Assessment of border delineation		
	Internal morphology of lesions		
	The secondary objectives of this study are to:		
	Demonstrate non-inferiority for number of lesions		
	Confidence in diagnosis		
	 Compare the 0.075 mmol/kg BW dose of gadobutrol to standard dose gadoterate (Dotarem) for: 		
	o T1w MRI image quality in a paired comparison		
	 Sensitivity/Specificity for presence of malignant disease versus the final clinical diagnosis. 		
	Compare the overall contrast enhancement of gadobutrol (0.075 mmol/kg BW) to the standard dose of gadoterate 0.1 mmol/kg) for steady-state CNS imaging. Quantitative contrast enhancement will be performed using an exploratory Overall Contrast Enhancement Estimation Algorithm.		
	 Assess the safety profile of the reduced dose of 0.075 mmol/kg BW of gadobutrol and standard dose gadoterate after IV administration 		
Test drug(s)	gadobutrol (Gadovist®/Gadavist®) 1.0 molar		
Name of active ingredient	gadobutrol		
Dose(s)	0.075 mmol/kg		
Route of administration	IV		
Duration of treatment	single dose		
Reference drug(s)	gadoterate (Dotarem®/Clariscan™) 0.5 molar		
Name of active ingredient Dose(s)	gadoterate 0.1 mmol/kg		
Route of administration	IV		
Duration of treatment	single dose		

26 MAR 2019	Version no. 2.0	Page: 6 of 60
Indication	Contrast-enhancement in MRI of the central nervol detection/visualization of areas with normal and dibarrier (BBB) and/or abnormal vascularity	
Diagnosis and main criteria for inclusion /exclusion	Adult patients with known or highly suspected CN contrast-enhanced MRI of the CNS based on currer on a previous imaging procedure.	
Study design	Open label multi-center comparative, cross-over triwith known or highly suspected of having CNS paimaging of the CNS.	
Methodology	Two CNS MRIs will be obtained for each enrolled	patient:
	 Unenhanced MRI consisting of steady-sta (T1-weighted, T2-weighted, and FLAIR) MRI consisting of steady-state sequence (and gadoterate-enhanced
	Unenhanced MRI consisting of steady-sta (T1-weighted, T2-weighted, and FLAIR) MRI consisting of steady-state sequence (and gadobutrol-enhanced
	The unenhanced MRI, combined unenhanced and a MRI, and the unenhanced, and the combined unenlenhanced MRI will be evaluated by 3 independent primary efficacy endpoints.	hanced and gadobutrol-
	The investigator will note the referring diagnosis, a location of the enhancing lesion which makes the s inclusion. The investigator will also provide the fin whether this represents malignant disease. The fina be based on all available clinical information up to MRI.	subject eligible for study nal clinical diagnosis and al clinical diagnosis will
	All AEs from the signing of informed consent will be assessed using data from treatment emergent ad	
Type of control	Gadoterate-enhanced MRI	
Number of patients	Total: 180 enrolled patients	
	Minimum per center: N/A Maximum per center:	~ 20
Primary variable(s)	The 3 primary efficacy variables (visualization par	ameters) are:
	the degree of lesion contrast enhancement	
	assessment of lesion border delineation, as	nd
	internal morphology of lesions	
Time point/frame of measurement for primary variable(s)	The primary variable requires completion of a bline sessions	ded read, done in three

26 MAR 2019 Version no. 2.0 Page: 7 of 60

Plan for statistical analysis

Co-primary target variable(s):

- Lesion contrast enhancement
- Lesion border delineation
- Lesion internal morphology

Up to 5 of the largest lesions will be selected and scored using a pre-specified scale by the blinded readers.

The related statistical hypotheses read as follows:

• H_0 : (gadobutrol - gadoterate) \leq -0.2*(gadoterate - unenhanced) vs.

 K_0 - H_1 : (gadobutrol – gadoterate) > -0.2*(gadoterate – unenhanced)

The study is considered successful if all 3 hypotheses related to these coprimary target variables can be rejected at a one-sided alpha of 0.025, which will be equivalent to a two-sided alpha of 0.05.

Rejection of such a hypothesis means that it is demonstrated that gadobutrol (Gadovist) at reduced dose preserves at least 80% of the effect gadoterate (Dotarem) as compared to unenhanced images.

NSF Nephrogenic Systemic Fibrosis
PID patient identification number
PPS per protocol analysis set
SAE serious adverse event

SDMB study data management book

SH sponsor's formulation code numbering system

SI signal intensity

TEAE treatment-emergent adverse event

TESAE treatment-emergent serious adverse event

T1 longitudinal relaxation time

T1w T1-weighted

T2 transversal relaxation time

T2w T2-weighted TMF trial master file

WHODD World Health Organization Drug Dictionary

26 MAR 2019 Version no. 2.0 Page: 13 of 60

3. Introduction

The constant evolution of magnetic resonance (MR) systems with faster sequences, functional imaging, and multichannel technology necessitates a contrast agent with the potential to benefit from these technical advances.

Gadobutrol (Gadovist) was first developed for the indication "contrast enhancement in cranial and spinal MRI" in doses of up to 0.3 mmol/kg BW.

First approved in Switzerland in 1998, gadobutrol has since been approved in more than 100 countries worldwide (including the European Union countries, USA, Japan, Canada, Australia, South Africa, Mexico, New Zealand, Turkey, and several Eastern European and Asian countries). In addition, gadobutrol has proven to be an effective contrast medium for all of its approved indications (CNS, MR angiography, liver and kidney, other body regions) and has exhibited an excellent safety profile, comparable to that of other marketed extracellular gadolinium based contrast agents.

The ideal extracellular gadolinium-based contrast agent (GBCA) for MRI would have a favorable safety profile and a low risk of potential long-term deposition within normal tissue. In this regard, macrocyclic agents GBCA (e.g. gadobutrol, gadoteridol, or gadoterate meglumine) that have higher in-vitro and in-vivo stability and longer dissociation half-lives are reasonable alternatives. The standard dose for all marketed GBCAs, including gadobutrol and gadoterate, is 0.1 mmol/kg BW regardless of each agent's relaxivity.

This study is designed to examine if a 75 percent dose of gadobutrol (0.075 mmol/kg), which has a high relaxivity, is noninferior to a 100% dose of gadoterate (Dotarem) (0.1 mmol/kg) for steady state CNS imaging.

4. Study objectives

4.1 Primary objectives

The primary objective of this study is to demonstrate noninferiority of gadobutrol-enhanced CNS imaging (at a dose of 0.075 mmol/kg) compared to gadoterate (0.1 mmol/kg BW) - enhanced CNS imaging (at a dose of 0.1 mmol/kg) for 3 lesion visualization parameters (degree of contrast enhancement, assessment of border delineation, and internal morphology of lesions) based on a blinded read.

4.2 Secondary objectives

The secondary objectives of this study are to:

- Demonstrate noninferiority for number of lesions based on a blinded read
- Confidence in diagnosis
- Compare the 0.075 mmol/kg BW dose of gadobutrol to standard dose gadoterate for:
 - o T1w MRI image quality in a paired blinded comparison

26 MAR 2019 Version no. 2.0 Page: 14 of 60

- o Sensitivity/Specificity for presence of malignant disease based on a blinded read
- Compare the overall contrast enhancement of gadobutrol (0.075 mmol/kg BW) to the standard dose of gadoterate (0.1 mmol/kg) for steady-state CNS imaging. Quantitative contrast enhancement will be performed using an exploratory Overall Contrast Enhancement Estimation Algorithm.
- Assess the safety profile of the reduced dose of 0.075 mmol/kg BW of gadobutrol and standard dose gadoterate after intravenous (IV) administration.

5. Study design

5.1 Design overview

This study is a Phase 4, multicenter, controlled, cross-over study with corresponding blinded image evaluations in male and female patients at least 18 years of age, who are referred for a contrast-enhanced MRI of the CNS based on a known or highly suspected lesion of the CNS.

Patients will undergo an unenhanced and contrast-enhanced MRI of the CNS using gadoterate at the standard dose of 0.1 mmol/kg BW. If the investigator does not identify an enhancing lesion of the CNS, then this patient will be considered a screening failure. If an enhancing lesion is identified, then the patient will undergo a second unenhanced and contrast-enhanced MRI of the CNS using gadobutrol at a dose of 0.075 mmol/kg BW.

Safety will be assessed from the first administration of gadoterate through 24 hours after the second administration of gadobutrol. Adverse events will be collected from the signing of informed consent through the end of the follow-up period. Serious adverse events (SAEs) will be followed through resolution. Patients who receive only the first MRI scan (considered screening failures) will be followed for SAEs only.

Gadobutrol will be administered at the dose of 0.075 mmol/kg body weight by single IV injection at a rate of 2 mL/sec, followed by 20-mL 0.9% saline flush at the same rate. Gadoterate will be administered at the approved standard dose of 0.1 mmol/kg body weight by single IV injection at 2 mL/sec, followed by 20-mL 0.9% saline flush at the same rate. The 2 injections will be separated by at least 24 hours, but not more than 15 days.

During the course of the study, 2 MRIs will be obtained from each patient as follows: before the administration of each of the contrast agent (unenhanced MRI) consisting of steady-state sequences (T1w, T2w, and FLAIR), following the gadoterate injection (gadoterate-enhanced MRI) consisting of steady-state sequences T1; and following the gadobutrol injection (gadobutrol-enhanced MRI) consisting of steady-state sequences (T1w).

The unenhanced MR image set, combined unenhanced and gadobutrol-enhanced MR image sets, and the unenhanced and combined unenhanced and gadoterate-enhanced MR image sets will be evaluated by 3 independent blinded readers. The blinded readers will also evaluate the

26 MAR 2019 Version no. 2.0 Page: 15 of 60

gadobutrol-enhanced T1w images compared to the gadoterate-enhanced T1w images in a paired read for image quality.

The final clinical diagnosis will be determined by the site investigator using all available clinical information up to 30 days post the first MRI. This final clinical diagnosis will be utilized as the standard of truth for the blinded assessment of diagnostic performance (sensitivity/specificity for malignant disease).

The safety of the patients will be assessed by monitoring of adverse events and treatment emergent adverse events (TEAEs).

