6.3 Exclusion criteria

A patient will be excluded from the study if he/she:

- 1. Has no enhancing lesion visible on the gadoterate-enhanced MRI scan.
- 2. Is pregnant or breast feeding
- 3. Has received any investigational product or has participated in any other clinical trial within 30 days prior to enrolling in this study
- 4. Has any contraindication to the MRI examinations or the use of gadolinium-containing contrast agents
- 5. Has a history of severe allergic or anaphylactic/anaphylactoid reaction to any allergen including drugs and contrast agents
- 6. Has received any gadolinium-based contrast agent < 24 hours prior to the study MRIs, or is scheduled to receive any contrast agent within 24 hours after the second study MRI
- 7. Is considered clinically unstable
- 8. Has severe cardiovascular disease (eg, known long QT syndrome, acute myocardial infarction [< 14 days], unstable angina, congestive heart failure New York Heart Association class IV or acute stroke (< 48 hours)
- 9. Is expected or is scheduled to have a change in any treatment or procedure between the gadoterate and gadobutrol MRIs that may alter image comparability
- 10. Is scheduled or is likely to require a biopsy or any interventional therapeutic procedure from the first study MRI up to 24 hours after the second study MRI

26 MAR 2019 Version no. 2.0 Page: 18 of 60

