- ^h The final clinical diagnosis will be recorded by the investigator within 30 days of the first study MRI.
- i Within 1h of injection

26 MAR 2019 Version no. 2.0 Page: 26 of 60

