11.4.2.3 Identification of benign or malignant disease

The investigator determines if the patient has benign or malignant disease.

The presence or absence of malignant disease in each patient for both contrast agents will be determined by the blinded readers, as well as the majority blinded reader (at least 2 of 3 readers), and compared to the investigators' assessment to calculate sensitivity and specificity for each drug.

Sensitivity, specificity, and accuracy for each drug will be compared using a McNemar's test with a noninferiority margin of 10 percent.

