6.2.3.3 Identification of benign or malignant disease

Up to 30 days post first MRI the site investigator will record in the eCRF his final clinical diagnosis, see Table 6–2 and if it confirms that the subject has malignant disease. This will serve as SOT for malignancy. A summary of final clinical diagnosis will be presented for total subjects in FAS and PPS.

The BRs will evaluate the presence of malignant lesions for each subject for the combined unenhanced and gadobutrol-enhanced MR image sets, and the combined unenhanced and gadoterate-enhanced MR image sets separately.

Page: 22 of 29:

The SOT will be compared to the blinded read evaluations individually and per majority of BRs (at least 2 out of 3 readers).

Table 6–2: Final clinical diagnosis of CNS lesions

Meningioma Chordomas • Anaplastic/malignant meningioma Primary lymphoma Glial tumor, low grade (I/II) Dermoid/Epidermoid tumors . Glial tumor, high grade (III/IV) Infectious disease (e.g., brain abscess, . cisticercosis, etc.) Glial tumor, tumor grade cannot be Venous angiomas • determined Metastases Meningeal spread of meningiomas (dural • involvement) Multiple sclerosis (acute and chronic) Cerebellopontine angle tumors . **Optic neuritis** Von Hippel Lindau syndrome Meningeal disease (focal enhancement) Hypertensive leukoencephalopathy Pituitary adenomas (macro and micro) Subacute/chronic ischemia • • Craniopharyngiomas Encephalitis • • Tumors of the choroid plexus Others, specify Tumors of the pineal gland Not assessable . Meningeal carcinomatosis Oligodendrogliomas grade II Oligodendrogliomas grade III (anaplastic/malignant)

Abbreviations: CNS = central nervous system

Diagnoses of the presence or absence of malignant tumors in each subject will be evaluated for consistency with the final diagnosis. Proportions of diagnoses consistent with the final diagnosis regarding malignancy will be calculated for gadobutrol and gadoterate, and a CI based on McNemar's test for the difference of these proportions will be given. The noninferiority of gadoterate to gadobutrol will be claimed using a noninferiority margin of 10%. These analyses will be performed for sensitivity, specificity, and overall accuracy.

Table 6–3 displays the components of the definitions for sensitivity, specificity, and accuracy.

Reader Response for MRI	Final clinical diagnosis (Standard of truth)			
	Malignant	Not Malignant		
Malignant	True positive (TP)	False positive (FP)		

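### The malignancy standard of truth can rest partly on the study MRIs under test, and its basis is not recorded (secondary accuracy comparison only)

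*Protocol*

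**What the plan says.** Protocol 5.1 defines the reference: "The final clinical diagnosis will be determined by the site investigator using all available clinical information up to 30 days post the first MRI". It then gives its use: "This final clinical diagnosis will be utilized as the standard of truth for the blinded assessment of diagnostic performance". Protocol 11.4.2.3 has the blinded reads "compared to the investigators' assessment to calculate sensitivity and specificity for each drug", with a noninferiority margin of 10 percent for sensitivity, specificity and accuracy. SAP 6.2.3.3 says of the same investigator diagnosis: "This will serve as SOT for malignancy".

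Timing is set in four places.

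- A footnote to the schedule in Protocol 9.1: "The final clinical diagnosis will be recorded by the investigator within 30 days of the first study MRI".
- Protocol 5.1: "The 2 injections will be separated by at least 24 hours, but not more than 15 days".
- Exclusion criterion 10 (Protocol 6.3) keeps out anyone scheduled for, or "likely to require a biopsy or any interventional therapeutic procedure from the first study MRI up to 24 hours after the second study MRI".
- Protocol 6.4 adds that no biopsy should take place between the two examinations.

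The SAP removes some truths. Under 4.4, a final diagnosis of *not assessable* leaves the analysis of diagnoses. Under 6.2.3.3, truths of *other* and *not assessable* leave the McNemar analysis.

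**The concern.** A reference standard should be independent of the tests it judges. Here the person who sets the truth is unblinded (Protocol 7.4) and has read the gadoterate scan to decide eligibility (Protocol 5.1). The schedule places the final diagnosis after the second study period, when both scans exist. No section asks for histology or follow-up, removes the study images from the evidence, or masks whoever sets the truth.

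Protocol 10.6 justifies blinded readers on the ground that investigators' diagnoses might be swayed by other clinical information. That protects the reads but not the reference, and the two share images.

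At stake is the comparison of sensitivity and specificity, a stated secondary objective. Where the study images set the truth, a lesion missed on both scans can be recorded as not malignant. It then leaves the sensitivity denominator and counts as a true negative for both agents. The difference between agents can shrink, or a difference can appear where there is none, depending on which scan the investigator relied on. No planned field shows which, so the bias could not be assessed from the planned data.

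**Working it through.** The plan gives no figure for this point, so there is none to reproduce. The check has two parts.

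**1. Time left for new histology.** The inputs are the gap between injections (1 to 15 days), the end of the criterion 10 period (24 h after the second MRI) and the truth cut-off (day 30 after the first MRI). Days left = 30 - (gap + 1).

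| Second MRI | Criterion 10 period ends | Days left | Share of window covered |
|---|---|---|---|
| Day 1 | Day 2 | 28 | 2/30 = 7% |
| Day 15 | Day 16 | 14 | 16/30 = 53% |

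The window for new histology is shortened, not closed.

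**2. Possible effect on the difference between agents.** Every accuracy input here is an assumption, because the documents give none. Let w be the share of patients whose truth status is taken from the images; in the rest it is correct. Assume that blinded readers reproduce the image impression and that impressions are independent given the true state.

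*Case A, both scans set the truth, disagreements split evenly.* Prevalence is 50%, sensitivity 85% for gadoterate and 70% for gadobutrol, and specificity 80% for both.

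- Both scans positive: 0.5 × 0.85 × 0.70 + 0.5 × 0.20 × 0.20 = 0.3175
- Gadoterate only positive: 0.5 × 0.85 × 0.30 + 0.5 × 0.20 × 0.80 = 0.2075
- Gadobutrol only positive: 0.5 × 0.15 × 0.70 + 0.5 × 0.80 × 0.20 = 0.1325
- Positive by image-based truth: 0.3175 + 0.5 × (0.2075 + 0.1325) = 0.4875
- Of these, called positive on gadoterate: 0.3175 + 0.5 × 0.2075 = 0.42125
- Of these, called positive on gadobutrol: 0.3175 + 0.5 × 0.1325 = 0.38375
- Gap under image-based truth: 0.42125 - 0.38375 = 0.0375
- Gap under correct truth: 0.5 × (0.85 - 0.70) = 0.075

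Apparent sensitivity difference = -[(1 - w) × 0.075 + w × 0.0375] / [(1 - w) × 0.5 + w × 0.4875].

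| w | Calculation | Difference (points) |
|---|---|---|
| 0 | -0.075/0.5 | -15.0 |
| 0.25 | -0.065625/0.496875 | -13.2 |
| 0.50 | -0.05625/0.49375 | -11.4 |
| 0.75 | -0.046875/0.490625 | -9.6 |
| 1 | -0.0375/0.4875 | -7.7 |

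The value crosses -10 at w = 0.025/0.03625 = 0.69. These are expected point differences. A noninferiority claim also needs the confidence limit to clear the margin.

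*Case B, only the gadoterate scan sets the truth, w = 0.25.* Both agents have 75% sensitivity and 75% specificity, and prevalence is 50%.

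- Both scans positive: 0.5 × 0.75² + 0.5 × 0.25² = 0.3125
- Gadoterate positive: 0.5 × 0.75 + 0.5 × 0.25 = 0.5
- Recorded truth positive: 0.75 × 0.5 + 0.25 × 0.5 = 0.5
- Gadoterate sensitivity: (0.75 × 0.375 + 0.25 × 0.5)/0.5 = 81.25%
- Gadobutrol sensitivity: (0.75 × 0.375 + 0.25 × 0.3125)/0.5 = 71.875%
- False difference: 71.875 - 81.25 = -9.4 points

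If both scans feed the truth in Case B, there is no false difference, but both sensitivities read too high: 78.1% at w = 0.5.

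**The case against.** The strongest defence is that an investigator's composite clinical diagnosis is an openly stated choice, that the affected comparison is only secondary, and that the documents already provide safeguards. Much of this stands.

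- No sentence says that the study MRIs belong to the truth. That is an inference from unrestricted wording and from the investigator's own read of the first scan.
- Criterion 10 is an eligibility rule. A reader might infer that it defers biopsy in enrolled patients or prevents histology. It does neither: 14 to 28 days remain, and inclusion criterion 1 admits known pathology, so some patients may have histology from before the study.
- An investigator without enough evidence can record *not assessable*, which takes the subject out. This does not help where a definite status was recorded from the images. The SAP also mentions a truth panel at this point, but neither document describes one, so it cannot be relied on as independent adjudication.
- The blinded readers are different people without clinical history. The dependence runs through shared images, not a shared reader. The illustration, which lets readers reproduce the image impression, therefore leans towards a larger effect.
- The direction is open. Reliance on the gadoterate scan alone works against gadobutrol. It is also the less natural case, since the schedule puts the diagnosis after the second period, though no earliest date is set.

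Nor does pairing remove the problem in general. The bias cancels in the difference only in special cases, such as equal agents with symmetric use of both scans.

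**Conclusion.** The point holds as a cheap improvement to the secondary sensitivity, specificity and accuracy comparison. The truth can rest partly on the images under test, and nothing planned would show how often it does.

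The size cannot be computed from the documents. Under the assumptions shown, a true -15.0 points would appear as -11.4 to -7.7 if both scans set the truth in 50% to 100% of patients. A false -9.4 would arise if the gadoterate scan alone set it in 25%. Other accuracies, correlated reads or a smaller image-based share would change these values.

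A reader might infer that accuracy is judged wholly against the study images, or that the bias favours gadobutrol. The documents support neither, because the share of image-based truths and the scan relied on are both unknown. A reader might also extend the concern to the trial's success criterion. That rests on three co-primary visualization scores, which do not use this truth.

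**What to change.** 1. In Protocol 9.2.6 and the eCRF, record the basis of each malignancy status: histology or cytology, pre-study diagnosis, other non-study evidence, or study MRI only.
2. In SAP 6.2.3.3, keep all subjects with an assessable truth as the main analysis. Add a prespecified sensitivity analysis in subjects whose truth does not rest on the study MRIs. State that this subset is smaller and may carry verification bias, because patients with suspicious images are more likely to have tissue. For that reason the noninferiority claim should not move to the subset.
3. Count the 30-day cut-off for the final diagnosis from the second study MRI. Every patient then has (gap + 30) - (gap + 1) = 29 days after the criterion 10 period. This lets later results enter the truth but does not take the images out of it, so it complements items 1 and 2.

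The cost is one eCRF field, a short SAP addition and one extra analysis. Last-patient-last-visit, which Protocol 5.5 ties to the final diagnosis, moves by at most 15 days. No added procedure or reader is needed.
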